**Part C:**

Part C will consist of a 52-week period of reduced burden safety assessments, for subjects in the EU countries. Subjects can only enter Part C once they have entered and completed Part B. The Part B EOT will coincide with Part C Visit 1 for those subjects who are willing to continue with the 52-week reduced burden safety assessment period.

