#### **8.4. Safety Endpoints**

The following safety endpoints will be assessed in Part A:

- Incidence of adverse events, serious adverse events, severe adverse events, drug-related adverse events, adverse events leading to withdrawal during the following periods:
  - Overall
  - During titration
  - During long-term treatment
- Observed values and changes from baseline in clinical laboratory parameters (hematology, chemistry, and urinalysis)
- Observed values and changes from baseline in vital signs
- Observed values in ECG parameters and abnormal findings
- Number of subjects with on-treatment QTcF values >450 ms, >480 ms, >500 ms, or a change from Baseline in QTcF of >30 ms or >60 ms
- Observed values and changes in UPDRS Part III (motor examination), BARS, HADS, C-SSRS, ESS, and MoCA©
- Duration of time to achieve stable dosing of SD-809

The following secondary safety endpoints will be assessed in Part B:

- Incidence of adverse events, serious adverse events, severe adverse events, drug-related adverse events, and adverse events leading to withdrawal
- Observed values and changes from start of randomized withdrawal in clinical laboratory parameters (hematology, chemistry, and urinalysis)
- Observed values and changes from start of randomized withdrawal in vital signs
- Observed values in ECG parameters and abnormal findings
- Number of subjects with on-treatment QTcF values >450 ms, >480 ms, >500 ms, or a change from Baseline in QTcF of >30 ms or >60 ms
- Observed values and changes in UPDRS Part III (motor examination), BARS, HADS, C-SSRS, ESS, and MoCA©

The following secondary safety endpoints will be assessed in Part C:

- Secondary safety endpoints:
  - Incidence of adverse events, serious adverse events, severe adverse events, drug-related adverse events, and adverse events leading to withdrawal from start of Part C
  - Observed values and changes in vital signs from start of Part C
  - Observed values and changes in C-SSRS from start of Part C
  - Observed values in ECG parameters and abnormal findings from start of Part C

- Number of subjects with on-treatment QTcF values >450 ms, >480 ms, >500 ms, or a change from Baseline in QTcF of >30 ms or >60 ms from start of Part C

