## 8.7. Sample Size

Because this is an open-label safety study, the sample size is not based on statistical considerations.

During the Randomized Withdrawal Period in Part B, there will be up to 194 subjects randomized (SD-809 or placebo). It is estimated that approximately 91 subjects per arm will enable a power of at least 90% to detect a beneficial effect of 1.4 points or more in the change

from pre-withdrawal to post-withdrawal in centrally read AIMS when the SD-809 arm is compared to placebo, assuming a standard deviation of 2.9 and a 2-sided type I error rate of 5%. Approximately 102 subjects may enroll in Part C conducted in the EU countries.

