## **INTRODUCTION**

This Statistical Analysis Plan (SAP) describes the planned analysis and reporting for Teva Branded Pharmaceutical Products R&D, Inc. study SD-809-C-20 (An Open-Label, Long-Term Safety Study of SD-809 [Deutetrabenazine] for the Treatment of Moderate to Severe Tardive Dyskinesia), and was written in accordance with SOP GBP\_RD\_702 (Statistical Analysis Plan).

The reader of this SAP is encouraged to read the study protocol for details on the conduct of this study, the operational aspects of clinical assessments, and the timing for completing the participation of a patient in this study.

The SAP is intended to be in agreement with the protocol, especially with regards to the primary and all secondary endpoints and their respective analyses. However, the SAP may contain more details regarding these particular points of interest, or other types of analyses (eg other endpoints). When differences exist in descriptions or explanations provided in the study protocol and this SAP, the SAP prevails; the differences will be explained in the Clinical Study Report.

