### **2.5.3. Final Analyses and Reporting – Part A and B**

Final analyses for Part A and B of this study will be performed after the last patient that enrolled into Part B has completed Part B of the study.

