#### **5.1.2. Patient Disposition**

Patients in the ITT population, patients in the ITT population but not treated, patients in the safety population, patients in the randomized withdrawal ITT and randomized withdrawal mITT populations, patients who completed Parts A and B and the study, patients who withdrew from Parts A and B and the study, and patients who enrolled in Part C will be summarized using descriptive statistics. Patients who withdrew from Parts A and B and the study will also be summarized using descriptive statistics by reason for withdrawal.

The Part A visit when patients enrolled in Part B will be summarized using descriptive statistics.

Patients reaching each Part A visit will be summarized using descriptive statistics.

Reasons for withdrawal by Part A visits using the categories prior to week 54 visit, week 54 visit to before week 106 visit, and week 106 visit to before week 145 visit will be summarized using descriptive statistics.

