## **7. SAFETY ANALYSIS**

### **7.1. Part A**

#### **7.1.1. General**

The safety population will be used for all safety summaries. Summaries will be presented by parent study treatment group and overall. Summaries will be presented for Parts A and B combined unless otherwise noted.

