**9. CHANGES TO PROTOCOL SPECIFIED ANALYSES**

ECG variables at each visit will not be analyzed in this study.

**APPENDIX A. SMQ CATEGORIES ADVERSE EVENTS AND ADVERSE EVENTS OF INTEREST**Depression (excl suicide and self injury) (SMQ) – narrow search

Activation syndrome  
Adjustment disorder with depressed mood  
Adjustment disorder with mixed anxiety and depressed mood  
Agitated depression  
Anhedonia  
Antidepressant therapy  
Childhood depression  
Decreased interest  
Depressed mood  
Depression  
Depression postoperative  
Depressive symptom  
Dysphoria  
Electroconvulsive therapy  
Feeling guilty  
Feeling of despair  
Feelings of worthlessness  
Helplessness  
Major depression  
Menopausal depression  
Post stroke depression  
Postictal depression  
Postpartum depression

Suicide/self-injury (SMQ) – narrow search

Completed suicide  
Depression suicidal  
Intentional overdose  
Intentional self-injury  
Poisoning deliberate  
Self-injurious behaviour  
Self-injurious ideation  
Suicidal behaviour  
Suicidal ideation  
Suicide attempt

Akathisia (SMQ) – narrow and broad search

Akathisia  
Extrapyramidal disorder  
Hyperkinesia  
Hyperkinesia neonatal  
Motor dysfunction

Movement disorder  
Psychomotor hyperactivity  
Restlessness

Parkinson-like events (SMQ) – narrow and broad search

Action tremor  
Akinesia  
Bradykinesia  
Bradyphrenia  
Cogwheel rigidity  
Drooling  
Dysphonia  
Extrapyramidal disorder  
Freezing phenomenon  
Gait disturbance  
Hypertonia  
Hypertonia neonatal  
Hypokinesia  
Hypokinesia neonatal  
Masked facies  
Micrographia  
Mobility decreased  
Motor dysfunction  
Movement disorder  
Muscle rigidity  
Muscle tone disorder  
Musculoskeletal stiffness  
On and off phenomenon  
Parkinson's disease  
Parkinson's disease psychosis  
Parkinsonian crisis  
Parkinsonian gait  
Parkinsonism rest tremor  
Parkinsonism  
Parkinsonism hyperpyrexia syndrome  
Postural reflex impairment  
Postural tremor  
Resting tremor  
Tremor  
Tremor neonatal  
Walking disability

Somnolence and sedation – preferred terms

Sedation  
Somnolence  
Sopor  
Stupor

Lethargy

Torsade de pointes/QT prolongation (SMQ) – narrow and broad search

Cardiac arrest  
Cardiac death  
Cardiac fibrillation  
Cardio-respiratory arrest  
Electrocardiogram QT interval abnormal  
Electrocardiogram QT prolonged  
Electrocardiogram U-wave abnormality  
Electrocardiogram repolarization abnormality  
Long QT syndrome  
Long QT syndrome congenital  

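### The protocol sets Part C safety endpoints, but the available SAP text plans no Part C safety summary, and its period definitions would class on-drug Part C adverse events as follow-up

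*Protocol*

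**What the plan says.** The protocol describes Part C in its synopsis: "Part C will consist of a 52-week period of reduced burden safety assessments, for subjects in the EU countries". Patients stay on SD-809 and must first have completed Part B. On size, protocol 8.7 says "Approximately 102 subjects may enroll in Part C conducted in the EU countries".

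Protocol 8.4 then states "The following secondary safety endpoints will be assessed in Part C" and lists adverse event incidence (all, serious, severe, drug-related, leading to withdrawal), vital signs, C-SSRS, ECG findings and counts above QTcF thresholds. Protocol section 8 leaves analysis detail to the SAP.

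The SAP introduces itself as the plan for study SD-809-C-20 and adds: "When differences exist in descriptions or explanations provided in the study protocol and this SAP, the SAP prevails". Its endpoint list (2.2.1) covers Parts A and B. In the available text Part C is named only in the disposition section (5.1.2): "patients who enrolled in Part C will be summarized using descriptive statistics". For safety, SAP 7.1.1 says "Summaries will be presented for Parts A and B combined unless otherwise noted", and SAP 7.2 covers Part B. The only change declared in Section 9 is "ECG variables at each visit will not be analyzed in this study".

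SAP 4.5 sets the analysis periods. For patients in both Parts A and B, the Maintenance Period ends on the day of the Part B open-label end-of-treatment visit. The Follow-up Period runs from the end of treatment, so defined, to the end of the study.

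**The concern.** Long-term safety is the study's first objective, and some Part C patients will have the longest exposure in the programme. After Part C Visit 1 the schedule drops UPDRS, BARS, HADS, ESS, MoCA and laboratory tests. Adverse event reports, vital signs, C-SSRS and ECGs are then the main remaining safety data. Late parkinsonism, akathisia or depression would be seen mostly through adverse event reports.

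Those are the data without a stated plan. The period definitions make this more than a lack of detail. An event in a patient still taking SD-809 in Part C falls, by definition, in a period meant for time after treatment. It would be missing from the on-treatment rates and could appear in the follow-up table instead.

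**Working it through.** **1. Protocol endpoints against SAP content.** For each Part C group in protocol 8.4, the SAP provides:

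- Adverse events: summaries for Parts A and B combined (7.1.3) and for the Part B withdrawal period (7.2.3). None for Part C.
- Vital signs: Part A visits (7.1.6) and Part B visits (7.2.5). None for Part C.
- C-SSRS: Part A visits and any time postbaseline, under the Parts A and B scope (7.1.11), and Part B visits (7.2.7). None for Part C.
- ECG findings: shifts to Part A visits (7.1.7) and Part B visits (7.2.6). None for Part C.
- QTcF thresholds: postbaseline counts (7.1.7), under the Parts A and B scope. None for Part C.

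Timing does not explain this. Amendment 07, which added Part C, is dated 02 May 2018. The SAP refers in the past tense to a data cut of 1 December 2018, and it mentions Part C.

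**2. Where Part C time goes.** The longest nominal exposure through Part B is 158 + 1 + 12 = 171 weeks, which is also the SAP's top exposure category (7.1.2). Part C takes the maximum to 171 + 52 = 223 weeks. SAP 7.1.3 uses patient-years in Parts A and B combined for event rates and exposure-adjusted incidence rates (EAIR), and censors Kaplan-Meier curves at the end of treatment in Parts A and B. It also plans a separate follow-up adverse event table. Under 4.5, Part C adverse events recorded by the data cut meet the follow-up definition. If the Parts A and B scope in 7.1.1 is taken to override that, they appear in no table. The text does not say which applies, and neither outcome is a Part C summary.

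**3. Size.** The documents give no patient-year figure; the 102 is a headcount with no derivation to reproduce.

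- Ceiling, all 102 enter and complete: 102 × (52 × 7) / 365.25 = 101.7 patient-years.
- Scaled to actual randomization: protocol 8.7 gives 102 beside up to 194 randomized, and SAP 2.3 reports 143. Assuming the same proportion enters, 102 × 143 / 194 = 75.2 entrants, or 75.2 × 364 / 365.25 = 74.9 patient-years.
- Dropout: no Part C rate is given. If 0% to 30% drop out evenly over the year, the multiplier runs from 1 to 0.85. The ceiling case then ranges from 101.7 down to 86.4, and the scaled case from 74.9 down to 63.7.

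These are totals of treatment time. An EAIR denominator would be smaller, because a patient with an event counts only up to the first one.

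**4. How much lies beyond Week 158.** For a patient entering Part B at Week w, Part C runs nominally from Week w + 13 to w + 65. The Part C weeks beyond 158 are therefore w − 93, with a floor of 0 and a cap of 52:

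- w = 93 or earlier: 0
- w = 106: 13
- w = 132: 39
- w = 145 or 158: 52

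A Week 158 entrant has 13 weeks beyond Week 158 in Part B and 52 in Part C, so 52 / 65 = 80% of that late exposure is outside the planned rates. For entrants at Weeks 106 to 145, Part B ends by Week 158 and essentially all of it is in Part C.

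**The case against.** The best answer is that reporting is staged. SAP 2.5.3 is headed for Parts A and B and says "Final analyses for Part A and B of this study will be performed after the last patient that enrolled into Part B has completed Part" (meaning Part B). Part C runs 52 weeks further, so it cannot be complete then, and a later Part C report is a natural reading. The SAP front pages are not available and might state such a scope. This stands in part. A reader might infer that Part C will never be analysed, and the documents do not support that. They show only that the available text does not say where it will be reported. Staging also does not repair the Follow-up definition, which applies at the Part A and B analysis.

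Second, protocol 8.3 already promises descriptive safety summaries, and SAP silence need not override protocol 8.4. That is fair, but 8.3 sets no Part C period or denominator.

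Third, the QTcF wording in 8.4 mentions both Baseline and the start of Part C, so a reader might infer that the reference is undefined and that prolongation already present on drug could be hidden. Protocol 8.3 largely answers this by fixing the SD-809-C-20 Baseline for change statistics. What remains is a wording point.

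Fourth, Section 9 is not wholly silent on Part C. Its ECG statement is study-wide, so it reaches the Part C observed ECG values. It does not reach the other groups.

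Fifth, the endpoints are secondary and descriptive, Part C was added to continue therapy, and data collection and serious adverse event reporting are unaffected. This limits the stakes. EAIR by time band is an SAP choice that the protocol does not require, but once chosen it should count on-drug time correctly.

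**Conclusion.** The point holds for specification. Five protocol endpoint groups have no Part C summary in the available SAP text, no other analysis is named, and the omission is undeclared. The SAP 4.5 definitions would also misplace on-drug Part C adverse events if read literally.

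The exposure affected is at most about 102 patient-years, and about 75 before dropout if entry scaled with randomization. The true figure depends on EU location, Part B completion and Part C retention, none of which the documents report. A reader might infer that all of this time is at the longest exposure. It is not: eligible stable patients could enter Part B at any study week, and those entering by Week 93 nominally contribute nothing beyond Week 158.

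This should be corrected. It does not affect the Part B efficacy comparison.

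**What to change.** 1. Amend SAP 4.5 so that Part C on-drug time is a treatment period and is excluded from Follow-up.
2. Add descriptive Part C tables for the five protocol 8.4 groups, with QTcF change taken from the SD-809-C-20 Baseline as protocol 8.3 already states. Alternatively, name in Section 9 the separate analysis that will report them.
3. When Part C data are complete, repeat the EAIR by time band, for all adverse events and for the SMQ categories, with Part C on-treatment time added.

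The cost is a short SAP amendment, some programming that largely reuses the Part A and B tables, and a data cut later than the Part A and B final analysis. No new visits or assessments are needed.

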## 8.5. Efficacy Measures

The following efficacy measures will be assessed during Part A:

- The change in AIMS score (items 1 through 7) from Baseline of this study at each visit that this is measured, as assessed by the site rating.
- The proportion of subjects who are a treatment success based on the CGIC at each visit that this is measured. A treatment success is defined as Much or Very Much Improved on the CGIC from Baseline of this study.
- The proportion of subjects who have a 50% or greater reduction in AIMS score from Baseline of this study at each visit that this is measured.
- The change in the modified CDQ-24 score from Baseline of this study at each visit that this is measured.
- The proportion of subjects who are a treatment success based on the PGIC at each visit that this is measured. A treatment success is defined as Much or Very Much Improved on the PGIC from Baseline of this study.
- The percent change in AIMS score from Baseline of this study at each visit that this is measured.

The following efficacy measure will be assessed during Part B (Randomized Withdrawal Period):

- Primary efficacy endpoint: change from Pre-withdrawal Visit AIMS scores (items 1 through 7) as assessed by blinded central video rating to the Post-withdrawal Visit between subjects treated with SD-809 and subjects treated with placebo.

## 8.6. Efficacy Analysis (Randomized Withdrawal Period; Part B)

Analysis of the change in centrally read AIMS score (items 1 through 7) during the Randomized Withdrawal Period (from the Pre-withdrawal Visit to the Post-withdrawal Visit) will use an analysis of covariance (ANCOVA) model with the change in AIMS score as the dependent variable. The model will include randomized withdrawal treatment group, AIMS score at the Pre-withdrawal Visit, and DRA status at the Pre-withdrawal Visit as fixed effects. The least squares means of the change in AIMS score will be compared between the SD-809 treatment and placebo groups using a 2-sided test at the  $\alpha=0.05$  level of significance. In addition, actual values and changes in AIMS score will be summarized using descriptive statistics.

The primary efficacy analysis will be tested at the  $\alpha=0.05$  level. If less than 135 subjects are enrolled into the randomized withdrawal portion of the study, inferential statistics will not be provided as the study will be insufficiently powered to detect a treatment effect given the sample size assumptions.

## 8.7. Sample Size

Because this is an open-label safety study, the sample size is not based on statistical considerations.

During the Randomized Withdrawal Period in Part B, there will be up to 194 subjects randomized (SD-809 or placebo). It is estimated that approximately 91 subjects per arm will enable a power of at least 90% to detect a beneficial effect of 1.4 points or more in the change

from pre-withdrawal to post-withdrawal in centrally read AIMS when the SD-809 arm is compared to placebo, assuming a standard deviation of 2.9 and a 2-sided type I error rate of 5%. Approximately 102 subjects may enroll in Part C conducted in the EU countries.

### **8.8. Protocol Deviations and Violations**

The Investigator is responsible for ensuring that the study is conducted in accordance with the protocol. No modifications to the protocol, other than those that are deemed necessary to protect the safety, rights, or welfare of subjects by the Investigator are to be made without prior, written approval by the Sponsor. The nature and reasons for the protocol deviation will be recorded where appropriate and indicated. The Sponsor must be notified of all protocol deviations/violations. Significant protocol deviations/violations (e.g., inclusion/exclusion criteria) will be reported to the Sponsor and to the IRB/IEC in accordance with its reporting policy.

### **8.9. Data Recording**

Source data will be transcribed onto source document worksheets and will then be entered into an eCRF. An Electronic Data Capture (EDC) system with eCRFs will be used for this trial. Instructions for eCRF completion will be provided in a separate document. Source data collection and entry into the eCRF will be completed by authorized study site personnel designated by the investigator. Appropriate training and security measures will be completed with the investigator and all authorized study site personnel prior to the study being initiated and before any data is entered into the eCRF system for any study subjects.

### **8.10. Data Quality Assurance**

Steps to assure the accuracy and reliability of data include the selection of qualified clinical Investigators and appropriate study sites, review of protocol procedures with the clinical Investigator and associated personnel prior to the study, and periodic monitoring visits by the Sponsor. The Sponsor (or designee) will review data accuracy and completeness during and after the study, and any discrepancies will be resolved with the clinical investigator or designee as appropriate.

### **8.11. Data Management**

The data will be entered into a validated EDC system that complies with Title 21 of the Code of Federal Regulations part 11, maintained by the Sponsor or designee. The data management group will be responsible for data processing, in accordance with agreed procedures. The Principal Investigator will electronically sign and date the appropriate eCRF page when instructed to do so by the study CRA. This signature will indicate that the Principal Investigator inspected or reviewed the data in the database, the data queries, and the site notifications, and agrees with the content.

The standard procedures for handling and processing eCRF records will be followed per Good Clinical Practice (GCP) and the Sponsor's (or designee's) SOPs. Complete details of data management will be described in a separate Data Management Plan.

## 9. ADMINISTRATIVE ISSUES

This protocol is to be conducted in accordance with the applicable GCP regulations and guidelines including the International Conference on Harmonization (ICH) Guideline on GCP. The clinical trial will be conducted in accordance with the applicable regulations of the local regulatory authority.

### 9.1. Investigator Obligations

#### 9.1.1. Independent Ethics Committee/Institutional Review Board Approval

Prior to initiation of the study, the written IEC/IRB approval of the protocol and Study Information Forms/Informed Consent Forms based on the International Conference on Harmonization (ICH) Good Clinical Practice (GCP) will be received. This approval will be on the Institutional letterhead and will refer to the Study Information Forms/Informed Consent Forms and to the study by title and protocol number given on page 1 of the protocol. A copy of the signed and dated letter of approval will be provided to Auspex and designee prior to study commencement. Any written information and/or advertisements to be used for volunteer recruitment will be approved by the IEC/IRB prior to use.

